The target patient population consists of 388 outpatients affected by hereditary haemoglobinopathies requiring chronic transfusion and chelation, randomized 1:1 in two groups of 194 patients each to ensure 310 evaluable patients. Chelation naïve and not naïve patients aged from 1 month to less than 18 years will be recruited. A staggered approach will be applied to patients aged less than 6 years (10% of the total sample), which will be recruited after results from the PK Study (Study DEEP-1, EudraCT n. 2012-000658-67) will be available.

Experimental arm: patients administered with DFP at 75-100 mg/kg/day for seven days per week. In patients aged less than 6 years the dose will be defined according to the results of the PK Study (Study DEEP-1, EudraCT n. 2012-000658-67). DFP daily dose will not exceed 100 mg/kg.

Control arm: patients administered with DFX at 20-40 mg/kg/day as recommended by the currently approved European SmPC (last update 10/08/2011). DFX daily dose will not exceed 40 mg/kg.

Details on the starting dose and subsequent dose adjustments are reported in **Section 6**.

The **treatment duration** for both groups is 12 months.

4.1Non-inferiority margin

This study is designed to demonstrate the **non-inferiority** of a new liquid DFP (80 mg/mL) formulation in comparison with DFX in terms of percentage of successfully chelated patients as described in **Section 4.3**.

DFP will be declared non inferior to DFX if the lower limit of the 95% confidence interval for the difference in the proportion of successful chelation in the two groups is above -12.5%. The choice of this margin is based on clinical considerations starting from the available evidences for the effects of DFX at both ferritin and cardiac levels. For details please refer to **Section 11**.

4.2Choice of comparator

DFP will be compared to the oral chelating agent DFX. The rationale for comparing two oral chelators derives from the recent literature data reporting that oral chelating agents currently represent the most widespread adopted therapy in the paediatric age, due to good compliance, improved QoL and reduced burden of the disease (Ceci A et al, 2011).

4.3Primary endpoint

The primary endpoint will be the measure of treatment efficacy defined as the percentage of patients successfully chelated, as assessed by serum ferritin levels (in all patients) and cardiac MRI T2* (in patients above 10 years of age able to have an MRI scan without sedation).

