9. INTERRUPTION OF TREATMENT

This section deals with a patient's premature withdrawal from the study before completing all scheduled visits. An individual subject may be withdrawn at the discretion of the responsible investigator and the study team for the reasons listed hereby. In the event one or more subjects are withdrawn, additional subjects may be enrolled to ensure an adequate number of subjects complete the cohort.

Reasons that a patient must discontinue participation in a clinical study are considered to constitute one of the following:

1. unsatisfactory therapeutic effect (quarterly increase in ferritin levels of at least 1500 ng/ml as detected by two determinations performed at no more than two weeks interval, or if cardiac MRI T2* decreases under 10ms)
2. subject's condition no longer requires study treatment
3. DFX treatment at 10 mg/kg/day (for safety reasons) for more than 4 weeks
4. DFP or DFX administration suspended (for safety reasons) for more than 4 weeks
5. adverse event(s) requiring change of chelation therapy, including moderate or severe Neutropenia
6. significant protocol violation
7. subject/legal guardian withdrew consent/assent
8. lost to follow-up
9. administrative problems
10. death

In the absence of a medical contraindication or significant protocol violation, the investigator may make an effort to keep the subject in the study. Should a subject withdraw or be withdrawn by the legal guardian, he/she has to complete a full set of the 'end-of-study phase assessments', i.e. a full V16 evaluation. Relevant records will have to be done on the corresponding CRF pages.

This requirement does not refer to patients who passed the screening and washout period and were found not to be eligible for treatment.

Patients prematurely withdrawn from the treatment will be considered treatment failures.

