11.2 Study population

Intent to treat population

For the intent to treat (ITT) analysis all patients that have been randomized and start therapy will be included.

Per protocol population

Patients in the per protocol (PP) population for the primary efficacy analysis (PP1) are those that have received the study drugs and for whom the composite endpoint is available at baseline and after 1 year treatment, without major protocol violations.

For the secondary efficacy evaluation assessed as non-inferiority of DFP to DFX in terms of serum ferritin levels the PP population (PP2) includes only patients for whom the measure of serum ferritin is available at baseline and after 1 year treatment.

For the secondary efficacy evaluation assessed as non-inferiority of DPF to DFX in terms of successfully chelated patients according to cardiac MRI T2* the PP population (PP3) includes only patients for whom the measure cardiac MRI T2* is available at baseline and after 1 year treatment.

Safety population

The population for the safety and tolerability analysis will include all patients having received at least one dose of study medication.

PK and PKPD population

The population for the pharmacokinetic and subsequent exploratory analyses (e.g. correlation between systemic exposure and ferritin levels) will include patients who have received the investigational drugs throughout the duration of the study (i.e., 1 year) and have had a blood sample collected for the assessment of drug concentrations in plasma.

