11.6 Efficacy evaluation

Primary efficacy

The primary efficacy evaluation will be based on a treatment success rate defined in Section 4.3 Primary endpoint. The primary analysis will be based on the PP1 population.

In addition, an ITT analysis will be performed to corroborate the findings. If no composite endpoint is estimable at 1 year treatment (unavailability of serum ferritin and/or MRI determination either at baseline or after 1 year treatment), the subject is considered a treatment failure in the ITT analysis. Non-inferiority will be assessed based on the two sided 95% confidence interval $[\delta_L, \delta_U]$ of the difference $\delta = p_1 - p_2$, being p_1 and p_2 the proportion of success in the n_1 and n_2 patients randomised to DFP and DFX arms, respectively. Non-inferiority will be claimed if δ_L is greater than -0.125. The two sided 95% confidence interval for δ will be estimated based on asymptotic normal approximation for the difference of two binomial probabilities as follows:

$$(p_1 - p_2) \pm Z_{1-\alpha/2} \sqrt{Var(p_1 - p_2)}$$

where Z_γ is the γ^{th} percentile of the standardised normal distribution and

$$Var(p_1 - p_2) = p_1(1 - p_1)/n_1 + p_2(1 - p_2)/n_2$$

If non-inferiority of DFP to DFX is established based on the PP1 population and the confidence interval for the null hypothesis of non-inferiority based on the ITT population is similar or the percentage of success for DFP is greater than that of DFX in magnitude, the hypothesis that DFP is superior to DFX in terms of the defined success criteria will be tested at the one-sided alpha level of 0.025. Superiority testing will be based on the ITT population. The rationale for superiority is justified by the known beneficial effects of DFP at the cardiac level.

Secondary efficacy

Efficacy measured through serum ferritin levels

Serum ferritin will be analysed as secondary measure of treatment efficacy. Serum ferritin is a well validated and clinically widespread surrogate measure of iron load, highly correlated with iron in the liver. It represents an easy to assess parameter in the paediatric population.

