11.12 Sample Size and power considerations

Primary efficacy objective

Assuming type I and type II errors of 0.025 and 0.20, respectively, and a one-sided test, and under the assumptions that the expected proportion of subjects declared treatment successes in the DFX arm is 65%, and the expected proportion of subjects declared treatment successes in the DFP arm is 67.5% a sample size of 310 subjects, randomized in a 1:1 ratio to DFP or DPX will yield 80% power to demonstrate non-inferiority of DFP versus DFX. Taking into account a possible dropout rate of about 20% a total enrolment of 388 patients aged from 1 month to less than 18 years are expected to be included in the trial.

Secondary efficacy objective

Sample size requirements for the secondary efficacy objectives (non-inferiority in terms of ferritin levels and cardiac MRI T2*) are provided in the following.

Based on published literature, testing for non-inferiority is appropriate also when comparing DFP to DFX efficacy in terms of serum ferritin levels. In this case, considering a hypothesis testing on the continuous measure, a non inferiority margin of 400 ng/ml is considered a reliable estimate of the true allowed maximum difference between the IMPs in order to assume DFP to be non-inferior to DFX in controlling iron overload in patients affected by hereditary haemoglobinopathies. The standard deviation of the differences is available by pooling findings from paediatric studies conducted in Europe and outside (El Alfay M et al., 2010), and a reliable and conservative estimate can be 1000 ng/mL.

On these assumptions, 310 evaluable patients are sufficient to provide at least 90% power to demonstrate non inferiority of DFP to DFX, assuming a type I error of 0.025 and a one-sided test.

When considering efficacy in terms of cardiac MRI T2*, less reliable estimates of treatment efficacy are available, especially in the paediatric population. However, there are no reasons for not assuming at least a non inferiority of DFP to DFX, considering also the known beneficial effects of DFP at the cardiac level. Based on the limited published figures of cardiac MRI T2* in the paediatric population and taking into account adult data, some plausible scenarios of sample sizes and related powers are provided in the following **Table 7**, assuming a type I error of 0.025 and a one-sided test. Detailed power curves will be provided in the statistical plan.

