11.13 Handling of missing data

A negligible amount of missing data is expected in this study because the patient population under study (patients affected by haemoglobinopathies requiring chronic transfusion and chelation therapy), and their parents, are accustomed to routine close monitoring in clinical visits, are used to frequent lab tests and comply with uncomfortable examinations (MRI), and are generally willing to participate in trials that may lead to increasing the availability of treatments. Moreover, the estimated treatment effect is not expected to be importantly biased in favour of the experimental treatment due both to the choice of the comparator and of the primary endpoint.

DFX is an oral chelator as DFP, and its compliance is expected to be comparable to that of DFP, or even better taking into account the once a day administration.

The completeness of the data that will allow the estimate of the primary endpoint (percentage of successfully chelated patients) is expected to be high due to the type of patients and condition.

Finally, patients who prematurely discontinue the trial for any reason will be considered treatment failures.

Assuming the worst scenario for incomplete data in order to provide conservative estimates for the trial results, the imputation of missing data will only apply to missing data because of a missing visit. This will affect the trend analysis for the secondary evaluation on serum ferritin levels. In this case, Linear Mixed Models (LMM) will be used as imputation method for missing data.

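### The general rule that withdrawn patients are failures conflicts with the PP1 definition; on the plain reading, lack-of-effect withdrawals drop out of the primary non-inferiority analysis

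*Combined protocol and SAP*

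**What the plan says.** Two places give a general rule with no analysis set attached. Section 9, after listing the reasons for leaving the study, states: "Patients prematurely withdrawn from the treatment will be considered treatment failures". Section 11.13, on missing data, states that "patients who prematurely discontinue the trial for any reason will be considered treatment failures".

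The analysis sections say something different. Section 11.2 defines PP1 as treated patients "for whom the composite endpoint is available at baseline and after 1 year treatment, without major protocol violations". Section 11.6 then says: "The primary analysis will be based on the PP1 population". ITT is there to corroborate. Where the composite cannot be derived, "the subject is considered a treatment failure in the ITT analysis"; no equivalent sentence exists for PP1.

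The sample size treats dropouts as not evaluable. Section 11.12 reads "Taking into account a possible dropout rate of about 20% a total enrolment of 388 patients", and Section 4 has patients "randomized 1:1 in two groups of 194 patients each to ensure 310 evaluable patients". Section 9 adds that where subjects are withdrawn, "additional subjects may be enrolled to ensure an adequate number of subjects complete the cohort".

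Reason 1 in Section 9 is unsatisfactory effect: a confirmed ferritin rise of 1500 ng/mL or more within a quarter, or cardiac T2* falling under 10 ms.

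**The concern.** Two statisticians could build different primary datasets from this text. One would apply Sections 9 and 11.13 and score early withdrawals as PP1 failures. The other would apply Section 11.2 and leave them out. The PP1 wording, the step from 388 to 310 and the replacement provision all favour the second.

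Reason 1 patients are not unknowns: they leave because chelation is seen to be failing. If they are dropped, the remaining success rate rises in each arm by an amount that depends on how many left. With clearly more such withdrawals on DFP, PP1 tilts towards non-inferiority. With equal numbers, or more on DFX, it tilts against DFP. ITT counts these patients, but Section 11.6 does not say what follows if PP1 clears the margin and ITT does not. Its only stated condition on ITT governs the later superiority test.

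**Working it through.** **Inputs.** From Sections 11.1, 11.6 and 11.12: success 65% DFX and 67.5% DFP, margin 12.5 points, one-sided 0.025, power 80%, 310 evaluable, 388 enrolled, Wald interval with unpooled variance. Reason 1 rates are not in the documents; the values below are assumptions over a range.

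**The plan's own figure.** n per arm = (1.960 + 0.842)² × (0.675×0.325 + 0.65×0.35) / (0.025 + 0.125)² = 155.9, so 156 per arm or 312 in total, against the stated 310. At 155 per arm the SE is √(0.446875/155) = 0.0537 and power is Φ(0.15/0.0537 − 1.960) = 79.8%. Enrolment is 310/0.80 = 387.5, so 388. The design reproduces, with dropouts removed from the evaluable number.

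**Are reason 1 patients failures by Section 4.3.1?** For baseline ferritin below 2500 ng/mL, the permitted rise is at most 15%, so less than 375 ng/mL; a 1500 rise from baseline fails. At 2500 or more, a 20% fall is needed; a rise fails. T2* dropping from 10 ms or more to below 10 ms fails criterion B on either branch. One qualification: the trigger is a rise over a quarter, so a patient who first fell well below baseline could meet it and still be under baseline. For such a patient, failure status comes from Section 9's rule rather than from Section 4.3.1.

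**PP1 false-claim rate.** Set the true rates, with reason 1 patients as failures, at the margin: 52.5% DFP v 65% DFX. Let t be the share withdrawn under reason 1, and let other dropout be random. The PP1 rate is then p/(1 − t), on n = 155(1 − t) per arm. The chance of a claim is Φ((difference + 0.125)/SE − 1.960).

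Example, 5% v 2%: 0.525/0.95 = 0.5526 and 0.65/0.98 = 0.6633, so the difference is −0.1106. With n = 147.25 and 151.9, SE = 0.0561. Then Φ(0.256 − 1.960) = 4.4%.

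| Reason 1, DFP v DFX | PP1 difference (points) | PP1 false claim |
|---|---|---|
| none | −12.5 | 2.5% |
| 2% v 1% | −12.1 | 3.0% |
| 5% v 2% | −11.1 | 4.4% |
| 10% v 5% | −10.1 | 6.2% |
| 5% v 5% | −13.2 | 1.9% |
| 10% v 10% | −13.9 | 1.4% |
| 5% v 10% | −17.0 | 0.3% |

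Break-even is where the PP1 difference is −12.5: t(DFP) = 1 − 0.525/(0.65/(1 − t(DFX)) − 0.125). For DFX 2%, 5% and 10% this gives 2.5%, 6.1% and 12.1%. PP1 therefore favours DFP only when its reason 1 rate exceeds about 1.2 times the DFX rate.

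**If ITT must also clear −12.5%.** Simulation, 1,000,000 trials, 194 per arm; other dropout is random, excluded from PP1 and a failure in ITT.

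| Reason 1, DFP v DFX | Both pass, no other dropout | Both pass, 20% other dropout per arm |
|---|---|---|
| 2% v 1% | 2.3–2.4% | 2.3–2.4% |
| 5% v 2% | 2.5% | 3.1% |
| 10% v 5% | 2.5% | 3.6% |

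ITT is not a full safeguard alone. With 20% random dropout its true difference shrinks to 0.8 × 52.5 − 0.8 × 65 = −10.0 points, and it passes about 7.0% of the time.

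**With reason 1 patients as PP1 failures.** The PP1 difference is −12.5 in every row, and the false claim is about 2.5%.

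**A case with no rule.** Suppose 49 DFP and 29 DFX patients of 194 withdraw for any reason, and completers succeed at about the planned rates. Completers only: 98/145 v 107/165, +2.7 points, lower limit −7.8. All withdrawals as failures: 98/194 v 107/194, −4.6 points, lower limit −14.6. One passes and the other does not.

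**The case against.** The strongest reply is that the plan already calls these patients failures. Sections 9 and 11.13 are general, and the second sits in the missing-data section. A reader might infer that the failure rule exists only for ITT; those two sentences contradict that. What stands is a conflict between sections, with ITT the only set expressly named.

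A reader might also infer that exclusion follows because the withdrawal visit (Section 7.2.5) includes no cardiac MRI. That fails for patients scored on ferritin alone, whose central ferritin is taken at withdrawal. In MRI patients, failing criterion A already settles the composite. The ground for exclusion is timing: there is no 1-year value.

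On size, reason 1 is a high bar. Section 11.12 uses an SD of 1000 ng/mL for ferritin change. If change were normal with mean zero, 6.7% would rise by 1500 over a whole year, and Section 6.3 allows dose increases well before that. Table 6 expects ferritin success of 76% on DFP and 57% on DFX, which points to more DFX failures and a conservative PP1. The 20% other dropout above also comes on top of reason 1 withdrawals; holding the total near the planned 20% gives joint rates of 3.0% (5% v 2%) and 3.2% (10% v 5%). All of this limits the size, but does not reconcile the rules.

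Finally, a reader might infer a loss of power to 57%, from reason 1 rates of 5% DFP v 10% DFX. That needs 67.5% and 65% to count reason 1 patients as failures already. Section 11.12 does not say so. If they are rates among evaluable patients, as the 310 suggests, PP1 power stays near 80%.

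**Conclusion.** The concern holds as an unresolved conflict between the general failure rule and the PP1 definition. Its plain reading removes lack-of-effect failures from the deciding analysis. Over the assumed unfavourable rates, the PP1 false-claim probability is 3.0% to 6.2% against 2.5%. It falls to about 2.3% to 3.6% if ITT must also pass, which the plan does not require. With equal rates, or more withdrawals on DFX, PP1 is conservative.

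These figures assume true rates at the margin, random other dropout, and reason 1 rates that the documents do not supply. They do not support saying that the plan favours DFP: the direction is unknown. The matter should be corrected because the fix is short and the choice should not be made once outcomes by arm are visible in an open-label trial.

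**What to change.** - Sections 11.2 and 11.6: state that patients withdrawn under reason 1, with baseline composite data and no other major protocol violation, are included in PP1 as failures.
- Sections 9 and 11.13: say which analysis set the failure rule covers for each other withdrawal reason.
- Section 11.6: claim non-inferiority only if the PP1 and ITT lower limits both exceed −12.5%.

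Cost: a few sentences and a small derivation, with no extra visits or samples and no change to the month-12 success definition. PP1 success rates may be slightly lower. Requiring both sets costs some power. In a simulation with 194 per arm, 20% random dropout in each arm, no reason 1 withdrawals and 67.5% v 65% success among the rest, PP1 passes 79.9% of the time and both sets pass about 75%. The sponsor should decide whether to accept that or enlarge the trial.

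Separately, and minor: Section 9 introduces one list of reasons both as discretionary and as mandatory. Choose one, and tabulate by arm who met reason 1 and whether they were kept or withdrawn.

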10. SPECIAL METHODS AND SCALES

10.1 Pubertal staging

Tanner scale:

- Male and female patients

I Preadolescent, no sexual hair

II Sparse, pigmented, long, straight, mainly along labia and at base of penis

III Darker, coarser, curlier

IV Adult, but decrease distribution

V Adult in quantity and type with spread to medial thighs

- Female patients, breast

I Preadolescent

II Breast budding

III Continued enlargement

IV Areola and papilla form secondary mound

V Mature female breast

11. STATISTICAL CONSIDERATIONS

11.1 General Design Issues

This is a multicenter trial primarily aimed at demonstrating the non-inferiority of DFP to DFX in terms of percentage of successfully chelated patients after one-year treatment.

A non-inferiority study is considered the appropriate design for this trial for the reasons outlined in **Section 4** and further detailed below. No studies directly comparing DFP and DFX are available, however extensive literature is published comparing the efficacy of both IMPs with DFO. In particular, DFP results as efficacious as DFO in reducing serum ferritin levels in several studies in adults and children (Olivieri et al, 1990; Olivieri & Brittenham, 1998; Aydinok et al, 1999, 2007; Maggio et al, 2002; Maggio et al, 2010; Gomber et al, 2004; Galanello et al, 2006; Ha et al, 2006; Pennell et al, 2006; Cappellini MD et al. 2006; Tanner et al, 2008; El-Beshlawy et al, 2008). Concerning DFX, a recent Cochrane review showed that an efficacy comparable to DFO can be achieved depending on the ratio of doses of DFO and DFX being compared; similar or superior efficacy for ferritin and LIC could only be achieved in the highly iron-overloaded subgroup treated at mean doses between 28 and 52 mg/day (Meerpohl JJ et al, 2012).

The analysis is based on a success criterion defined in terms of serum ferritin and cardiac iron load (see **Section 4.3**) applied to paediatric population affected by hereditary haemoglobinopathies requiring chronic transfusion and chelation.

A composite outcome measure including ferritin and cardiac MRI T2* is considered an updated and multi-factorial clinical evaluation of iron overload in this experimental population, as further detailed in **Section 4**. As cardiac MRI T2* evaluation is generally uninformative and burdensome under 10 years of age because of the need of sedation, the outcome measure has been tailored to the age of the patient at a threshold of 10 years.

A successfully chelated patient in this trial is hence defined as follows:

- a patient satisfying the criterion A in **Section 4.3.1** based on ferritin levels if the patient is < 10 years of age;
- a patient satisfying criterion A and criterion B in **Section 4.3.1** based on both ferritin levels and cardiac MRI T2* in patients \geq 10 years of age.

For ethical reasons, the sole criterion A will be applied also to patients \geq 10 years of age who would require sedation during the MRI assessment.

The choice of this composite endpoint allows the feasibility of the trial in the entire paediatric population and provides an up to date approach to the evaluation of the global iron accumulation in paediatric transfusion-dependent patients. In addition the use of a composite endpoint (rather than an alternative one) allows avoiding multiplicity while adequately characterising (total body iron load and in the heart) the beneficial effect of treatments.

Each component of the composite endpoint will be considered for secondary analyses with the intent to clarify the interpretation of the composite. For such analyses no adjustment for multiplicity will be foreseen (see **Section 11.2**).

Based on the above defined composite endpoint, non inferiority is established if the lower limit of two sided 95% confidence interval of the difference in success rate is above - 12.5%. The choice of this margin is based on clinical considerations starting from the available evidences for the effects of DFP and DFX on ferritin levels and cardiac iron load.

In details, the percentage of expected success for DFX and DFP measured as change from baseline to 1 year treatment is summarised in the following **Table 6**:

Table 6: Success rates for DFP and DFX

Serum ferritin levels	76% (95%CI: 63.6-88.5) DFP mean dose 66.4 mg/kg/day (Addis A et al, 1999) Paediatric population included in the meta-analysis but not analysed separately.	57% (95%CI: 50.7-63.3) DFX used at 20-30 mg/kg/day (Taher A et al, 2009) 75 adult and 162 paediatric patients
Cardiac MRI T2*	66% Higher percentage in splenectomised patients (Pennell DJ et al, 2006) 29 adults	69.5% in patients with moderate-to-mild baseline cardiac iron load (≥ 10 to <20 ms) DFX mean dose 33.1 \pm 3.7 mg/kg/day (Pennell DJ et al, 2010) 72 adult and 29 paediatric patients

Pooling together these findings, the expected percentage of success in the composite endpoint is assumed to be equal to 65% and 67.5% for DFX and DFP, respectively. The non inferiority margin of 12.5% has been considered to be a good estimate of an achievable lower bound of the true difference between the DFP and DFX.

Other secondary objectives include the evaluation of treatment efficacy in terms of liver iron concentration, the assessment of treatment safety and tolerability profiles, healthcare resources utilisation and patient global assessment and the analysis of the relationship of the demographic covariates and the disposition of DFP.

The correlation between DFP and DFX disposition and serum ferritin levels after 1 year treatment will be tested as exploratory objective of the trial.

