2. OBJECTIVES

2.1Primary Objective

The primary objective of this study is to assess the non-inferiority of deferiprone (DFP) compared to deferasirox (DFX) in terms of changes of ferritin levels and heart iron concentration in paediatric patients affected by hereditary haemoglobinopathies requiring chronic transfusions and chelation.

2.2Secondary objectives

Secondary objectives of this study are:

- to assess treatment efficacy in terms of ferritin levels
- to assess treatment efficacy in terms of cardiac MRI T2* in patients over 10 years of age able to perform MRI scan without sedation
- to estimate the efficacy of treatments in terms of liver iron concentration (LIC) measured by MRI in all paediatric subjects able to have MRI scan without sedation
- to evaluate the safety and tolerability profile of treatments
- to assess healthcare resources utilisation and patient global assessment, including compliance and quality of life (QoL) evaluation
- to confirm the influence of demographic covariates on the pharmacokinetic disposition of treatments across the study population.

2.3Exploratory objectives

Additional and exploratory objectives of the study include the assessment of the correlation between systemic exposure to the investigational drugs and serum ferritin levels observed after one year treatment.

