In details, a composite outcome measure will be defined as primary endpoint of the study according to patient's age, as follows:

- in patients < 10 years of age treatment success will be defined only in terms of serum ferritin level (criterion A);
- in patients ≥ 10 years of age treatment success will be defined in terms of both serum ferritin level and cardiac MRI T2* (criteria A and B).

In patients ≥ 10 years of age who would require sedation for the MRI scan, treatment success will be defined only in terms of serum ferritin level (criterion A). Details on the choice of the composite outcome are in **Section 11.1**.

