In the last years, the role of cardiac MRI T2* in the management of patients affected by hereditary haemoglobinopathies has been highlighted. Findings are available for the adult population, more limited experience is reported in children. Despite the importance of early detection of cardiac siderosis, MRI is difficult to perform in the paediatric population and it is usually uninformative in younger children (namely less than 10 years) due to late iron accumulation in the heart.

As a consequence, cardiac MRI T2* will be analysed as additional secondary measure of treatment efficacy in the subgroup of patients (over 10 years) for which the scan is available. It will be analysed as binary variable (successfully/unsuccessfully chelated patient according to the criterion 4.3.1 in Section 4.3) as part of the composite endpoint as well as according to its quantitative nature.

Due to the paucity of paediatric data on cardiac MRI T2*, descriptive statistics will be calculated and used to support efficacy conclusions. Descriptive measures will be listed by visit and treatment and characterised by frequency and percentage or mean, standard deviation, median, and quartiles.

However, considering the importance of improving knowledge on iron overload at the heart level in the paediatric population, a test for non inferiority of DFP to DFX in terms of cardiac MRI T2* (successfully/unsuccessfully chelated patient according to the criterion 4.3.1 in Section 4.3 Primary endpoint) will be performed whenever MRI evaluation will be available in at least 60-70% of the evaluable population. See section 11.3 different scenarios (non inferiority margins and sample size) related to this secondary efficacy assessment. The population for this analysis is the PP3.

Efficacy measured through MRI liver iron concentration

Iron overload in the liver compartment will be assessed as additional secondary measure of efficacy. LIC changes within one year will be evaluated in terms of percentage of successfully chelated patients according to the success criterium described in section 4.4.1 Secondary endpoints. LIC absolute values will be also analysed.

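### The primary objective names heart iron, but its only rule is a margin on the composite success rate, so meeting that rule does not support a separate heart-iron claim

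*Combined protocol and SAP*

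**What the plan says.** Section 2.1 sets the primary objective as non-inferiority of DFP to DFX "in terms of changes of ferritin levels and heart iron concentration". The design statement in Section 4 repeats both measures.

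The rule for that objective appears in Sections 4.1, 11.1 and 11.6. In 11.1, "non inferiority is established if the lower limit of two sided 95% confidence interval of the difference in success rate is above" -12.5 points. The success rate is the composite of Section 4.3: "in patients < 10 years of age treatment success will be defined only in terms of serum ferritin level (criterion A"). Patients aged 10 or over must meet both the ferritin criterion (A) and the T2* criterion (B), unless they would need sedation for the scan, in which case A alone applies. Section 6.6 fixes no number of patients per age group.

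Section 11.1 makes each component a secondary analysis, meant to help interpret the composite. In 11.6, ferritin has its own non-inferiority rule on mean change (-400 ng/mL). For T2*, "descriptive statistics will be calculated and used to support efficacy conclusions"; a formal non-inferiority test is added only if scans are available in at least 60-70% of evaluable patients. Table 7 shows T2* margins of -12.5 and -10 points as scenarios and selects neither. No section says what happens to the primary claim if a component result is unfavourable.

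**The concern.** The objective speaks of two measures and the rule tests one blended rate. T2* has no weight in ferritin-only patients. In scanned patients it changes the outcome only for those who also meet the ferritin criterion. Better ferritin results on DFP can therefore make up for worse T2* results inside the composite.

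The plan's own inputs make that pattern plausible. Table 6 gives DFP ferritin success as "76% (95%CI: 63.6-88.5) DFP mean dose 66.4 mg/kg/day", against 57% for DFX, and T2* success as 66% for DFP against 69.5% for DFX. If the composite rule is met and the conclusion is written in the words of Section 2.1, it asserts non-inferiority on heart iron without requiring any T2* result to support it.

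**Working it through.** **Inputs.** Section 11.12: "Assuming type I and type II errors of 0.025 and 0.20, respectively, and a one-sided test"; composite success assumed to be 65% on DFX and 67.5% on DFP; 310 evaluable patients, so 155 per arm. Table 6: ferritin success 76% (lower limit 63.6%) for DFP and 57% for DFX; T2* success 69.5% for DFX. Assumed, because the documents do not give them: the scanned share f, taken as 60-70%, and independence of criteria A and B.

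**The plan's own figure.** n per arm = (1.96 + 0.84)² × (0.65×0.35 + 0.675×0.325) / (0.125 + 0.025)² = 155.9, so 156 per arm or 312 in total, against 310 stated. 310/0.8 = 387.5, so 388 enrolled. An exact binomial sum of the stated rule (unpooled 95% lower limit above -0.125, 155 per arm) gives a 79.8% chance of meeting it at 67.5% v 65%, and 2.5% at 52.5% v 65%. The stated design reproduces.

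**Composite rate in an arm.** A(1 - f + fB), where A is ferritin success and B is T2* success. For example, with Table 6 ferritin, f = 0.6 and DFP 20 points worse on T2* (49.5% v 69.5%):

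- DFX: 0.57 × (0.4 + 0.6×0.695) = 46.6%
- DFP: 0.76 × (0.4 + 0.6×0.495) = 53.0%

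DFP leads the composite by 6.4 points despite the T2* deficit.

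**Chance of meeting the composite rule with a true 20-point T2* deficit** (exact sums, 155 per arm):

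| Ferritin success, DFP v DFX | f = 0.6 | f = 0.7 |
|---|---|---|
| 76% v 57% (Table 6) | 92.1% | 85.2% |
| 63.6% v 57% (DFP at its Table 6 lower limit) | 45.6% | 35.4% |
| 65% v 65% | 13.7% | 9.2% |
| Equal, set so that the DFX composite is the planned 65% | 7.6% | 3.7% |

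In the last row, ferritin success in both arms is 0.65/(1 - f + 0.695f), which is 79.6% at f = 0.6 and 82.6% at f = 0.7.

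**Dependence.** If A and B overlap as much as possible, the first row falls to 80.0% and 64.3%.

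**Comparison.** Tested alone against a 12.5-point margin with 93-108 scanned per arm (60-70% of 155), a true 20-point T2* deficit would pass about 0.1% of the time.

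**Why dilution alone does little at these shares.** With composite rates between 50% and 65%, the half-width of the interval is about 11 points. The observed composite difference must then be no worse than about -1.4 to -1.8 points. With equal 65% ferritin, a 20-point T2* deficit moves the composite by 0.65 × 0.6 × 20 = 7.8 points (f = 0.6) or 9.1 points (f = 0.7), and the rule usually fails.

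**The case against.** Several parts of the case against stand.

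- A reader might infer that the composite margin is the only decision rule in the plan. It is the only rule for the primary objective; 11.6 has secondary non-inferiority analyses for ferritin and, conditionally, for T2*. At 60-70% scanned, the T2* test would be run or would be close to its trigger. What is missing is any consequence of that test for the primary claim, and a selected T2* margin.
- A reader might infer that ferritin-only patients can by themselves carry a large T2* loss past the rule. At these shares they cannot: the chance is 9-14% with equal 65% ferritin, and 4-8% when calibrated to the planned composite. It rises to about 34% only if the scanned share is as low as 30% (equal 65% ferritin).
- The 85-92% result needs a true 19-point ferritin advantage, taken from an unmatched contrast between studies. It also implies a DFX composite of 45-47%, well below the planned 65%. The plan itself expects only a 2.5-point composite difference. When DFP truly leads on the composite, meeting the rule is the right answer for the composite.
- In scanned patients every T2* failure is a composite failure, so T2* is not ignored.
- Sections 4.1 and 11.1 already describe the aim as a difference in success rates. The loose wording is in 2.1 and in the design statement of Section 4.

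None of this supplies a rule linking the T2* result to the words on heart iron in the primary objective.

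**Conclusion.** The point holds as a mismatch between the primary objective and the rule that decides it. Meeting the rule supports non-inferiority on the composite success rate, not on heart iron separately. How much T2* loss can be offset depends almost entirely on the ferritin advantage: for a true 20-point deficit the chance of meeting the rule runs from 4-8% (no advantage, planned composite) through 35-46% (63.6% v 57%) to 85-92% (Table 6 rates). These figures rest on independent components, 155 per arm, DFX T2* success of 69.5% and 60-70% scanned. That last range is the trigger for the T2* test, not a scan share the plan predicts.

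A reader might conclude that the trial is likely to hide a large cardiac loss, or that a -12.5-point T2* condition must be added to the primary rule. The documents support neither. The high figures need an advantage the planners did not assume, Table 7 selects no T2* margin, and such a condition would trade power for a wider claim.

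**What to change.** 1. In Sections 2.1, 4 and 11.1, state that meeting the rule supports non-inferiority on the composite success rate only, and not on heart iron separately.
2. In Section 11.6, always report the criterion B success difference with its two-sided 95% CI in scanned patients, beside the primary result, whatever the scan availability.
3. Rest any separate heart-iron non-inferiority claim on that T2* analysis, with a margin the sponsor selects and justifies before database lock.

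The composite, its margin and the sample size do not change, and the scans are already scheduled. The cost is wording and one more interval. The primary claim becomes narrower, and a separate T2* claim would have limited power. With 93-108 scanned per arm and, for illustration, a 12.5-point margin, power is 72-79% at Table 7's 65/70, 46-52% with equal rates of 69.5%, and 26-30% at Table 6's 69.5/66 (DFX/DFP).
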